7.0 Data handling and record keeping

The use of personal addresses, emails and telephone numbers will be used to send potential participants information on the study, these will not be seen or used outside of the clinical care team until participants have consented and given the researcher their preferred method of contact.

All research data will be collected confidentially and as per Appendix 15: data sharing agreement, identifiable data will be stored on encrypted NHS servers. All identifiable data will be password protected to ensure maximum security, which only the research team will have access to. The data will then be anonymised and transferred to q:/ Drive on the

Sheffield Hallam University server which will only be accessible by the SHU research team. It will be transferred from nhs.net account to nhs.net account to ensure sufficient security is maintained. The Q drive is SHU's Research Store service and provides shared storage for currently active research projects. Data is backed up automatically on a daily basis and can be fully recovered in the case of accidents. All backups are securely kept on two remote locations for a period of 90 days. Access to all folders is restricted to researchers, students and external partners working on the project. Password-protection will be used on all data files to ensure only the research team have access.

Participants will consent to the use of photography video recording for the study, they will be made aware that no images taken will be used for dissemination or publicity without their further consent.

8.0 Access to source data

The sponsor will permit monitoring and audits by the relevant authorities, including the Health Research Authority and Research Ethics Committee. The investigator will also allow monitoring and audits by these bodies and the sponsor, and they will provide direct access to source data and documents.

9.0 Statistical Analysis

As this is a qualitative feasibility study, a sample size of 25 is adequate according to Lancaster et al as supported by NIHR when estimating a parameter within a study. This study is testing the effectiveness and viability of 'JIA Toolbox', we are looking at the practicalities of using these prototypes in real contexts and seeking clues as to the potential real-life impacts, by way of specifying further product design refinements and as a way of understanding how a future pilot evaluation study might be practically designed and which outcome measures would be relevant to service users, HCPs and device manufacturers.

At the conclusion of this study, the STOP/GO criteria for continuing onto a larger study will be:

- green light if 50% report a positive change in their condition management,
- amber light requiring potential changes if 30% report a positive change and,
- red light if only 10% report a positive change.

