3.0 Clinical need

Juvenile Idiopathic Arthritis (JIA) is a paediatric long-term condition affecting approximately 15,000 children and young people (CYP) in the UK, with 1,000-1,5000 new diagnoses each year. It causes ongoing joint inflammation, pain and stiffness, making everyday activities difficult. It affects every aspect of CYP's lives, impacting on physical, social, emotional and education development, with widespread lack of understanding often making CYP with JIA feel isolated. There are products designed to support CYP with JIA but they have limitations and our previous work (a survey and co-design process conducted in 2018) shows they are not sensitive to user needs. Our survey highlighted that CYP with JIA find these products difficult to use as most therapeutic aids are targeted towards an adult population. The few that are aimed at children were seen as patronising and stigmatising. These products also often neglect to take into account the wider stakeholder network such as parents, teachers and healthcare professionals, and therefore neglects to support them in helping CYP with JIA.

Key stakeholder groups (CYP with JIA, their parents, healthcare professionals and teachers) were active participants throughout our previous work, through co-design workshops and surveys. The key highlighted clinical need was assistance with self-management.

This is broken down into the following specific unmet needs:

- Pain-management. Improved pain management would enable CYP to do more of the things they love, by providing a solution that they can use independently as and when is needed, positively impacting their wellbeing.
- Physiotherapy adherence as currently CYP often do not do clinician-recommended exercises. Improved compliance with recommended physiotherapy interventions may reduce pain in the long-term and improve mobility.
- Communication between the pupil and teacher. Improving this communication would provide CYP with a way to discreetly access necessary support without facing stigma, improving their concentration by removing anxiety around accessing help

As a result, 'JIA Toolbox' was co-designed and developed to fulfil these needs and previously tested on a cohort of n=10 CYP with JIA during a proof-of-concept study. The results from

the proof-of-concept study were successful with 80% of participants finding one or more of the prototypes beneficial for their condition management.

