5.8 End of intervention interview (1 hour 1:1 with researcher)

WP6

6.1 Analyse qualitative data with healthcare professionals who are a part of the research team

The end of study is defined as the date of the last interview of the last participant.

As 'JIA Toolbox' consists of therapeutic self-management tools, participants will decide when to use the prototypes during the 3-month intervention period. As such, there should be no added burden to the participants in using these products, as they are designed to assist with condition management rather than hinder. There will be two training sessions, one on how to use the data collection packs (examples shown in appendix 3) and one on how to use the prototypes. This will ensure that the participants are clear on what they should do, minimising any potential risks in interacting with the prototypes. There will be regular weekly check ins to ensure participants are happy with the study and to troubleshoot any issues raised. The 3-month intervention period where the participants are using the devices will take place over August, September and October, giving CYP 1 month to get used to the devices prior to using them in a school context. From the previous proof-of-concept study, it was highlighted that the devices were beneficial in building CYP-teacher relationship near the beginning of the school year. Post-intervention interviews will be conducted at the end of the study to ensure all experiences are equally captured and to give participants the opportunity to highlight anything they feel needs additional clarification.

The study design has had input from YOUR RHEUM which is a group of CYP (11-24) with diagnosed rheumatic conditions, and JAR which is a group of CYP (7-25) with Juvenile Arthritis. Both groups regularly input on CYP rheumatology research. They have a strong track-record in advising on and shaping rheumatology research and represent a 'Gold Standard' approach to PPI involvement. These groups have been involved in shaping the study design and participant facing materials such as the data collection packs to ensure they are appropriate and will be effective. They have also commented on the prototypes themselves, feeling that they fulfill key unmet needs within the JIA population. [name] and [name] are both healthcare professionals who work within

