15.0 Outcomes

There are two overall outputs from this project:

- 1. Output:** Co-designed prototypes. The co-designed approach helps to ensure 'JIA Toolbox' will be useful, acceptable and of real benefit to the JIA community, improving chances of commercial success.
- 2. Output:** In depth data (symptom experience and prototype use patterns) from a larger cohort n=25 over a longer period (3 months). The feasibility study context enables early discovery of barriers to adoption and therefore can be addressed and rectified. It also helps build up a strong evidence base on the effectiveness and viability of these devices, enabling a good standpoint from which to leverage further funding.

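### The STOP/GO rule counts any reported improvement in condition management, with no requirement that the child used a prototype or credits one for the change

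*Protocol*

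**What the plan says.** Protocol section 9.0 fixes three outcomes for progression to a larger study: "green light if 50% report a positive change in their condition management", "amber light requiring potential changes if 30% report a positive change and" and "red light if only 10% report a positive change". None of the three mentions use of a prototype or a link between the change and a prototype. The rule also does not state who reports or what the denominator is. The same section says "a sample size of 25 is adequate".

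Section 5.0 leaves use to the children and families: "participants will decide when to use the prototypes during the 3-month intervention period". No minimum is set. The section provides training and weekly check-ins, and it judges impact by comparing baseline with the intervention period. No control group is described.

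Section 15.0 lists as an output "In depth data (symptom experience and prototype use patterns) from a larger cohort n=25", so information on use is planned. It does not enter the rule.

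Section 3.0 gives the proof-of-concept result, from 10 children, as "80% of participants finding one or more of the prototypes beneficial for their condition management". That measure named the prototypes. The STOP/GO measure does not.

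**The concern.** A self-directed device can fail simply by not being used. A child may leave the prototypes in the box, remain in the study to the final interview, and report that condition management has improved. The rule scores that child as a success.

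Improvement without use is plausible. Children must have current symptoms to enter, so some may improve over three months anyway, and every child receives weekly contact from the team. With no comparison group, nothing in the design separates such change from an effect of the Toolbox.

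The same weakness reaches users: a child who used a device but improved for unrelated reasons also counts. Non-use is the clearest case of a wider gap, which is that the rule does not tie the reported change to the intervention.

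At stake is what a green light means. The primary objective in section 4.0 concerns usage of the three prototypes and their impact. A green result under the present wording need not show either.

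**Working it through.** **Inputs from the protocol.** Planned sample 25. Thresholds 50% (green) and 30% (amber), both in section 9.0. The sample size is supported by a citation only, so there is no calculation of the plan's own to reproduce.

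**Inputs that are assumptions.** The number of non-users *k*, the improvement rate among users *u*, and the improvement rate among non-users *b*. The protocol gives none of them. I also read the denominator as all 25 children, since the rule states no restriction.

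**Step 1, cut-offs.** Green: 0.50 × 25 = 12.5, so at least 13 positives. Amber: 0.30 × 25 = 7.5, so at least 8.

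**Step 2, what the wording allows, without probabilities.**
- 11 improved users + 2 improved non-users = 13; 13/25 = 52%, green.
- Counting users only in the numerator: 11/25 = 44%, not green.
- A more extreme case with 15 users and 10 non-users: 7 + 6 = 13; 13/25 = 52%, green. Users only: 7/25 = 28%, below the amber line.

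**Step 3, chance of green.**
- As written: P[Bin(25 − k, u) + Bin(k, b) ≥ 13].
- Use-linked, denominator still 25: P[Bin(25 − k, u) ≥ 13].

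With *u* = 0.50 (assumed):

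| Non-users *k* | Use-linked | As written, *b* = 10% | *b* = 20% | *b* = 40% | *b* = 50% |
|---|---|---|---|---|---|
| 1 | 0.419 | 0.436 | 0.452 | 0.484 | 0.500 |
| 2 | 0.339 | 0.371 | 0.403 | 0.468 | 0.500 |
| 3 | 0.262 | 0.308 | 0.356 | 0.452 | 0.500 |
| 5 | 0.132 | 0.195 | 0.266 | 0.420 | 0.500 |
| 8 | 0.025 | 0.076 | 0.153 | 0.373 | 0.500 |

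The difference is small when non-use is rare and non-users seldom improve. It is large when several children do not use the devices and background improvement is common. In the last column non-users improve as often as users. That column shows the lack of attribution and of a control group more than a problem of non-use.

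**Step 4, how much a use condition alone would remove.** Take a background improvement rate of 20% (assumed) with 20 users and 5 non-users. Unrelated positives expected are 20 × 0.20 = 4 among users and 5 × 0.20 = 1 among non-users. A use condition removes only the 1. Tying the reported change to a prototype is what addresses the other 4.

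**The case against.** The strongest reply is that the surrounding text already ties the assessment to the devices. The research question asks about the impact of using the Toolbox, section 5.0 compares baseline with data gathered while the devices are in use, and section 9.0 speaks of the practicalities of use. Read in that light, the reported change is change with the Toolbox. This does not settle the matter. Those sentences describe the study's aim and a study period. They set no condition on what a given child must have done to be scored. Nor is this a detail left for an analysis plan: the protocol itself fixes the rule, and adding a use or attribution condition later would alter it.

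Several other objections stand in part:
- A reader might infer from section 3.0 that about 20% of children will be non-users. The documents do not support that. The remaining 20% of the 10 proof-of-concept children did not report benefit, which says nothing about whether they used the devices.
- A reader might infer that a false green is likely. The documents do not show this. Complete non-use with continued participation is possible, but training and weekly check-ins work against it and no rate is given.
- Better condition management is not the same as milder disease, so a lull in symptoms need not produce a positive report. That limits how often the path occurs but does not close it.
- Non-use is not ignored by the study as a whole, since use patterns and barriers to adoption are planned outputs. It is ignored only by the decision rule.
- A minimum-use threshold would have no basis in the documents and would sit badly with a pain device described in section 3.0 as used when needed. I do not propose one.

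**Conclusion.** The point holds as a fault in how a success is defined. The rule counts a reported positive change whether or not the child used a prototype and whatever the child thinks caused it. Use is discretionary and no control group is described, so a child who used nothing can help produce a green light.

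The fault follows from the wording and does not depend on any assumed rate. Its size does. On the assumption that users improve at 50%, it runs from negligible (0.436 against 0.419) to decisive (0.373 against 0.025), and the documents do not say where in that range the study will fall. These figures compare the present rule with a use condition only; the added effect of requiring attribution is not quantified. They also rest on reading the denominator as all 25 children, which is natural but not stated.

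The consequence is limited to a decision to proceed to a larger study. The correction is still worth making, because it changes what that decision can be said to show.

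**What to change.** In section 9.0, define a STOP/GO positive as a child who has any recorded use of at least one prototype during the intervention period and who reports a positive change in condition management that they attribute to one or more prototypes. Keep all enrolled children in the denominator and score non-users as not positive. Report the number of non-users, overall and for each prototype, beside the STOP/GO percentage. No minimum-use cut-off is needed.

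The cost is a sentence or two in section 9.0, an attribution question in the end-of-intervention interview, and a cross-tabulation of use against reported change. The use-pattern data are already planned, but the data collection packs should be checked to confirm that they record use child by child.

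There are two drawbacks. The STOP/GO percentage can only stay the same or fall. The attribution is self-reported, so it narrows the gap left by having no control group but does not close it.

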4.0 Study Objectives and Purpose

This is a feasibility study assessing the effectiveness and viability of Juvenile Idiopathic Arthritis (JIA) Toolbox in improving overall condition management by improving Children and Young People's (CYP's) independence and functional ability.

Each prototype was developed to address an unmet need and therefore has a specific aim:

- Prototype 1: A wearable device that aims to promote pain self-management skills;
- Prototype 2: A motivational tool that aims to improve physiotherapy engagement;
- Prototype 3: A wearable device that aims to promote discrete communication between CYP and teachers and other stakeholders.

The primary objective of this study is to explore the potential impact of 'JIA Toolbox' in addressing the unmet needs identified by stakeholders by conducting a feasibility study to explore the usage of the three prototypes and their impact on CYP's independence and functional ability.

The secondary objective is to collect contemporary data on CYP's experiences of living with JIA to inform future research and innovation.

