The process for recruiting and consenting teachers hinges upon which CYP have consented to be involved, as it is their teacher(s) that will need to be recruited. Once interested CYP and their parent/guardian have been consented. UA or CD will approach the CYP's school/teacher with a recruitment flyer for context. If interested, they will be given a participant information sheet. If they wish to proceed, a call will be arranged with the study lead UA for any queries. A consent form will then be emailed to be signed and sent back. If their teachers do not want to participate, this will still be useful data as it speaks to adoption of the intended prototypes. However, it is expected that at least 50% of CYP's teachers will engage with the study as the prototypes are designed to assist them in their role, in terms of helping and communicating with CYP. Based on the proof-of-concept study 100% of CYP's teacher's engaged, and we therefore expect similar engagement.

Families who participate in the study will receive a £50 'thank you' voucher recognising their time and involvement. The participation gift will be mentioned in the participant information sheet, once the participants have expressed an initial interest in WP4, after seeing the flyer. Teachers will not receive financial remuneration due to the fact that the prototype

pertaining to them is designed to assist duties that fall within the remit of their role in terms of helping and communicating with CYP.

Recruitment flyers, participant information sheets, consent and assent forms are shown in Appendix (5,6,7,8,9,10 and 11).

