11.0 Ethical Considerations

1. Risk of unintended distress

Discussion with participants about JIA will be treated sensitively. Interviews may lead to minor distress. To minimise this risk, participants will be informed they do not have to complete any questions or take part in any activities that make them uncomfortable and reminded that they have the right to withdraw at any point and will still receive their thank you voucher. If a participant becomes distressed, the session will be ended sensitively but quickly. Any participant who has shown evidence of distress will be discussed with the study clinicians (DH/CD). The rheumatology team has a clinical psychologist who could be involved if significant distress is felt to have occurred, although it is not anticipated this will be needed.

2. Burden of time

Involvement is optional and participants will receive a 'thank you' voucher. The use of the prototypes is designed to fit around day-to-day activities and to assist rather than be a burden. Difficulty in using the products will be minimised through training and weekly check ins where the project team can trouble shoot any queries.

3. Concern that they can't withdraw

Before each part of the study, participants, parents and guardians will be informed that this is a voluntary research study and they are free to withdraw at any point and it will not affect their future healthcare.

4. Risk of unintentionally worsening symptoms

The prototypes are designed to help improve symptoms and are based upon proven therapies and known and tested technologies that are routinely used in other products on the market, therefore this risk is minimal. Based on the proof-of-concept study, the prototypes were seen as beneficial to symptom manage and did not make any participants symptoms worse.

5. Using the prototypes

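### The STOP/GO rule uses one percentage of positive reports, so recruitment, completion and worsening cannot change the light, and it gives no result by device

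*Protocol*

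**What the plan says.** Section 9.0 of the protocol lists the STOP/GO criteria for moving to a larger study. There are three, all on the same quantity: "green light if 50% report a positive change in their condition management", amber at 30%, and red at only 10%. No other section adds a progression criterion. The section does not say whose report counts (child, parent or teacher), or whether the percentage is of those recruited, those completing or those interviewed.

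The same section describes the purpose in these terms: "we are looking at the practicalities of using these prototypes in real contexts". It adds that the study should inform how a later pilot is designed and which product refinements are needed.

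Section 4.0 states: "Each prototype was developed to address an unmet need and therefore has a specific aim". The aims are pain self-management, physiotherapy engagement and classroom communication.

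On worsening, Section 11.0 calls the risk minimal and reports that in the proof-of-concept study the prototypes "did not make any participants symptoms worse". Section 3.0 gives that study's size as 10 children. Section 10.0 refers to monitoring procedures and a risk assessment form, but nothing links either to the STOP/GO rule.

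**The concern.** A green light from a feasibility study will be taken as a sign that a larger study can be run and is worth running. Here the light responds to one thing only, the share of positive reports. A study that recruited poorly, lost most of its children, or left many of them worse could still be green. Sections 3.0 and 15.0 say the results will be used to seek further funding, so the light matters.

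The rule also returns a single answer for three devices. A sponsor who needs to know which prototype to refine gets no help from the light itself.

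**Working it through.** **Inputs.** Planned number: 25 children (Study Summary, Sections 3.0, 5.0 and 15.0). Green 50%, amber 30%, red 10% (Section 9.0). Three prototypes (Section 4.0). Proof-of-concept study: 10 children, none worse (Sections 3.0 and 11.0). The 50% is read as at least 50%. Section 9.0 supports the 25 by citation alone, with no rate or precision target, so there is no figure to reproduce; the points below do not depend on it. Intervals are exact (Clopper-Pearson) 95%.

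**1. Positives needed for green.** 0.50 × 25 = 12.5, so 13 of 25. Because the rule is a percentage with no minimum, 10 of 20, 5 of 10 or 3 of 5 is equally green.

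**2. Recruitment shortfall.** Suppose 10 children are recruited and 5 report positive change. 10/25 = 40% of target; 5/10 = 50%, green, with interval 19% to 81%. A smaller study also makes a misleading green more likely. The chance of green is the binomial probability of reaching the required count:

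| True positive rate | n = 25 (13 or more) | n = 10 (5 or more) |
|---|---|---|
| 30% | 1.8% | 15% |
| 40% | 15% | 37% |
| 50% | 50% | 62% |

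**3. Loss after recruitment.** Suppose 25 are recruited, 15 are lost, and 5 of the 10 interviewed are positive. With respondents as denominator this is 5/10 = 50%, green. With all recruited as denominator it is 5/25 = 20%, short of even the 30% amber figure. The undefined denominator alone decides the result.

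**4. Worsening.** With 25 reports, 13 better is 52% (interval 31% to 72%), green. The other 12 (48%) may be unchanged or all worse; the light is the same. The proof-of-concept result gives limited reassurance. With 0 of 10 worse, the upper limit for the true rate is 1 − 0.05^(1/10) = 26% (one-sided 95%) or 1 − 0.025^(1/10) = 31% (two-sided).

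**5. Devices.** If each of 13 positive reports is due to one device, the split could be 5, 4 and 4: 5/25 = 20% (interval 7% to 41%) and 4/25 = 16% (5% to 36%). The overall result is green, and nothing in it shows which device helped whom.

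**The case against.** The strongest reply is that the rule matches the declared target. The research question is about condition management overall, Section 2.0 presents the prototypes as working together, and Section 14.0 treats the Toolbox as one intervention with several parts. Different children may benefit from different devices, so one overall answer is defensible. This stands. A reader might infer that pooling is an error, or that each device should meet the 50% and 30% levels alone. The documents do not support that: those levels were set for the Toolbox as a whole, and the protocol does not define success for a single device.

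A reader might also infer that benefit from one device carries all three forward. Section 9.0 does not say so. It decides whether a larger study follows, not which devices enter it, and usage data and interviews can inform that choice outside the light.

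Third, the primary objective in Section 4.0 is potential impact, which the rule does address, and no stated objective names recruitment or retention rates. That is fair, and it makes this an improvement to the rule, not the repair of a contradiction. But Section 9.0 itself names practicalities and the design of the next study as purposes, and the only criteria for going on ignore both.

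Fourth, 12 of 25 worse is extreme: 48% lies above the 31% upper limit from the earlier 10 children. It shows what the rule allows, not what is likely. Harms may also be handled under the risk assessment form, which is not shown.

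Finally, Section 6.0 says "it is expected that at least 50% of CYP's teachers will engage with the study" and then, from full participation in the proof-of-concept study, that teachers "engaged, and we therefore expect similar engagement". A reader might see a conflict. There is none: the first is a floor, the second an expectation, and both can hold.

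**Conclusion.** The concern holds in a limited form. The protocol fixes a progression rule that recruitment, completion and worsening cannot influence, and whose denominator is open. This is not detail left to an analysis plan, because the criteria are stated in the protocol. As written, 13 better with 12 worse of 25 is green. So is 5 of 10 with 40% of the target recruited, whichever of recruited or interviewed children is the denominator. The case of 15 lost out of 25 is green only if respondents are the denominator. The rule also yields no device-level result, which is a gap in reporting and not a fault in the target.

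These conclusions rest on reading 50% as at least 50% and on Section 9.0 holding the complete set of criteria. The 5, 4 and 4 split additionally assumes one device per positive report. The point is worth acting on because the remedy is cheap and uses data the study already generates.

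**What to change.** In Section 9.0:

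1. Use all recruited children as the denominator for the positive-change percentage and state that number. A child with no end report then counts as not positive.
2. Add recruitment against 25, and completion of the end interview, as progression criteria required for green. The first item alone does not cover a recruitment shortfall. The documents give no basis for particular limits, so the sponsor should set them before data collection.
3. At the end interview, record better, same or worse. Report the number worse next to the number better, and require a review of worsening before green is declared. A fixed veto is not advised, because there is no control group and symptoms in JIA recur. For example, blocking green when more than 10% are worse (3 or more of 25) would do so about 46% of the time if background worsening were 10% (13% of the time at 5%, 75% at 15%; all three rates are assumptions).
4. Report benefit and use for each prototype beside the overall light, without gating on it. Show prototype 3 both among all children and among those with a participating teacher. Section 6.0 regards teacher refusal as information on adoption, and the second denominator alone would hide it.

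The cost is a few lines of text and one fixed question at an interview already planned. Green becomes somewhat harder to reach.
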